#### **9.6.1.2 Serious Adverse Events**

Each AE is to be classified by the Investigator as serious or nonserious. An AE that meets one or more of the following criteria/outcomes is classified as serious:

- Death
- Life-threatening (see below for definition)
- In-patient hospitalization or prolongation of existing hospitalization (see paragraph below on hospitalization)
- Persistent or significant disability/incapacity (see paragraph below on disability)
- Congenital anomaly/birth defect
- Is considered a medically important event not meeting the above criteria, but which may jeopardize a subject, or may require medical or surgical intervention to prevent one of the criteria listed in this definition.

Serious may also include any other event that the Investigator and Investigator-Sponsor judges to be serious. If there is any doubt whether the information constitutes an AE or SAE, the information is to be treated as an SAE.

**Life-threatening** – Any event in which the subject was at risk of death at the time of the event; ‘life-threatening’ does not refer to an event which hypothetically might have caused death if it were more severe. For example, drug-induced hepatitis that resolved without evidence of hepatic failure would not be considered life-threatening, even though drug-induced hepatitis of a more severe nature can be fatal.

**Hospitalization** – Hospitalization is defined as an overnight admission with observation of a minimum of 24 hours. A hospitalization planned before the start of the study for a pre-existing condition that has not worsened during the AE reporting period does not constitute an SAE unless an untoward event occurs related to the procedure (e.g., elective hospitalization for a total knee replacement due to a preexisting condition of osteoarthritis of the knee that has not worsened during the course of the study).

**Disability** – Defined as a substantial disruption in a person’s ability to conduct normal life functions.

**The following guidelines are to be used when reporting SAEs for this study:**

**Medical Diagnoses** – Whenever possible, a medical diagnosis term should be used to report SAEs instead of signs and symptoms due to a common etiology, as determined by qualified medical study staff. Signs and symptoms should be reported as event terms only when the medical diagnosis remains unknown and revised to a medical diagnosis term once it has been established.

**Procedures** – Diagnostic and therapeutic non-invasive and invasive procedures, such as surgery, should not be reported as SAEs. However, the medical condition for which the procedure was performed should be reported if it meets the definition of an SAE. For example, when a subject is hospitalized for an acute appendicitis that begins during the SAE reporting period, appendicitis should be reported as the SAE and the resulting appendectomy noted in the narrative.

Pre-planned therapeutic procedures or surgeries not associated with a new medical condition or worsening pre-existing condition should not be reported as SAEs.

The only procedures to be captured include the placement of dialysis access (e.g., Arteriovenous Graft or Fistula [AVG/ AVF], Peritoneal Dialysis [PD] Catheters, Central Venous Catheters [CVC]). Diagnostic procedures (e.g., x-rays, ultrasounds, echocardiograms) are not required to be captured.

**Transplantation** – It is anticipated that subjects may receive a kidney transplant during this study. Kidney transplant will be captured as a Study Endpoint and will not be recorded as an SAE. Adverse events resulting in prolongation of hospitalization during the index kidney transplant will be captured as an SAE. Subjects will discontinue study drug following receipt of a

kidney, other solid organ, hematopoietic stem cell or bone marrow transplant. Receipt of a kidney transplant will be considered an exception to the requirement for a 30-day safety follow up period, however any subject who receives a kidney transplant, and has not withdrawn consent from study participation, will have a vital status check performed at 30-days following the kidney transplant.

**Dialysis Initiation** - It is anticipated that subjects may initiate maintenance dialysis during this study. Dialysis initiation will be captured as a Study Endpoint and will not be recorded as an SAE. Hospitalization days will be recorded in the eCRF and adverse events resulting in prolongation of hospitalization during the index dialysis initiation will be captured as additional SAEs. Subjects will discontinue study drug following initiation of dialysis. Initiation of dialysis will be considered an exception to the requirement for a 30-day safety follow up period, however any subject who initiates maintenance dialysis, and has not withdrawn consent from study participation, will have a vital status check performed at 30-days following the initiation of maintenance dialysis.

## **9.6.2 Classification of an Adverse Event**

### **9.6.2.1 Severity of Event**

The Investigator will assess each SAE as either mild, moderate, or severe using the following guidelines to describe the maximum severity of the SAE:

- Mild: Does not interfere with subject's usual function. Clinical or diagnostic observation only; no intervention indicated.
- Moderate: Interferes to some extent with subject's usual function. Requires minimal, local, or noninvasive medical intervention/medication.
- Severe: Interferes significantly with subject's usual function. Disabling, medically significant but not immediately life-threatening; may include hospitalization or prolongation of hospitalization indicated.

Note that a **severe** AE is not necessarily a **serious** AE. For example, a headache may be severe in intensity, but would not be classified as serious unless it met at least 1 of the criteria for serious events listed above.

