## **9.6.6 Serious Adverse Event Reporting**

Any SAE, regardless of causal relationship, must be reported to the Investigator-Sponsor within 24 hours after the Investigator or designee becomes aware of the SAE. Compliance with this time requirement is essential so that the Investigator-Sponsor may comply with its regulatory obligations.

The initial SAE report should be completed as fully as possible but should contain, at a minimum:

- Subject number/ID, sex, and age/date of birth;
- The date of awareness;
- The date of report;
- Name of the reporter;
- Name of the suspected medicinal product, if applicable;
- A description of the event, including event term(s), seriousness criteria, and a clinical summary of the event;
- Causality assessment.

Information about all SAEs (either initial or follow-up information) should be collected and recorded in English on the electronic SAE Report Form within the EDC system. The Investigator must provide an assessment of causality (relationship to study drug). If the event meets serious criteria and it is not possible to access the EDC system, a study-specific paper SAE Report Form should be sent to the Investigator-Sponsor via email ([[contact]](mailto:[contact])) within 24 hours of being made aware of the SAE. When the EDC system becomes available, the SAE information must be entered within 24 hours of the system becoming available.

The Investigator must report follow-up information relating to an SAE to the Investigator-Sponsor by updating the electronic eCRF with the new information or by submitting a study-specific paper SAE Report Form in the event that the EDC is not available. When the EDC system becomes available, the SAE information must be entered. The subject should be observed and monitored carefully until the condition resolves or stabilizes.

All deaths are to be thoroughly investigated and reported. Autopsy reports and death certificates are to be obtained, if possible, and summarized as appropriate.

The Investigator-Sponsor and/or its designee are responsible for reporting SAEs to all applicable regulatory agencies and the central ethics committees within the required timeline.

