#### **Adverse Events of Special Interest:**

- Iron overload is defined as any liver biopsy findings or MRI imaging consistent with this diagnosis in the setting of persistent TSAT >45%.
- Clinically significant hypophosphatemia, defined as serum phosphorus <2.5 mg/dL.

No statistical inference testing will be done for adverse events.

AE analyses, by subject incidence and event counts, will be summarized by preferred terms, within system organ class, by number and percentage for all subjects in the safety population.

All SAEs will be coded using Medical Dictionary for Regulatory Activities (MedDRA). All verbatim terms will be reconciled to preferred terms by the Medical Monitor. Treatment-emergent SAEs will be summarized by system organ class and preferred term (PT) for each treatment group. SAEs will also be summarized by their maximum severity.

A summary and listing of all deaths and cause of death will be provided overall and by treatment group.

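### The three-grade SAE severity scale has no grade whose definition fits a life-threatening or fatal event, and no planned table shows non-fatal life-threatening SAEs by arm

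*Protocol*

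**What the plan says.** Protocol 9.6.2.1 (Severity of Event) sets a three-level scale and applies it to all SAEs: "The Investigator will assess each SAE as either mild, moderate, or severe using the following guidelines to describe the maximum severity of the SAE". The highest level covers events that interfere significantly with usual function, and its description continues: "Disabling, medically significant but not immediately life-threatening; may include hospitalization or prolongation of hospitalization indicated". No level above it appears in either document.

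Protocol 9.6.1.2 (Serious Adverse Events) sets the seriousness rule: "An AE that meets one or more of the following criteria/outcomes is classified as serious". The first two criteria listed are death and life-threatening events. Life-threatening is defined as "Any event in which the subject was at risk of death at the time of the event". Protocol 9.6.6 adds: "All deaths are to be thoroughly investigated and reported".

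On reporting, SAP 3.6.1 states: "SAEs will also be summarized by their maximum severity". Protocol 10.4.5.1 makes the same commitment. Neither says how to handle an SAE that falls outside the three definitions. SAP 3.6.1 also plans a summary and listing of deaths with cause, overall and by arm.

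**The concern.** The scale applies to SAEs, and the worst SAEs are the ones its top definition leaves out. This matters more here than in a trial that grades all adverse events. Non-serious events are generally not collected, apart from the two adverse events of special interest and a few other reportable situations. Protocol 11.9 rests safety oversight on SAE collection.

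A by-arm severity table is where a reader would look for a shift towards the gravest harm. If a life-threatening event shares a row with an admission that never put the subject at risk of death, the table cannot show that shift. For non-fatal events, no other planned table does so.

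**Working it through.** No arithmetic applies. The point concerns definitions and does not depend on any rate, sample size or event count. The check sets the seriousness criteria against the grade definitions, and then against the planned outputs.

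**Step 1: does each kind of SAE meet a grade?**

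| Kind of SAE (Protocol 9.6.1.2) | Mild | Moderate | Severe |
|---|---|---|---|
| Admission, never at risk of death | depends on the event | depends on the event | can fit; hospitalization is named there |
| Life-threatening, survived | no: this grade needs no intervention and no functional effect | no: this grade needs only minimal, local or noninvasive treatment | excluded by the wording on immediate threat to life |
| Fatal | no | no | excluded in the same way |

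Two details need checking.

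- *Whether* immediately life-threatening *in the grade means the same as* life-threatening *in the seriousness criteria.* It does in substance. The seriousness definition requires actual risk of death when the event occurred and rules out events that might hypothetically have been fatal.
- *Whether a fatal SAE that began less gravely could be graded on its onset.* It could not. Section 9.6.2.1 asks for maximum severity, and at its worst the event was lethal.

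**Step 2: do these events reach the severity summary?** Yes. Protocol 9.6.1.2 records dialysis initiation and kidney transplant as endpoints and not as SAEs, but makes no such exception for death or life-threatening events. Protocol 10.4.5.1 and SAP 3.6.1 summarize SAEs by maximum severity without excluding any.

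**Step 3: where else would they be visible by arm?**

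| Planned output | Fatal SAEs | Non-fatal life-threatening SAEs |
|---|---|---|
| Primary composite and the mortality component | yes | no |
| SAP 3.6.1 death summary and listing | yes | no |
| SAEs by system organ class and preferred term | included, not separated | included, not separated |
| Related SAEs | only if related, not separated | only if related, not separated |
| Maximum severity | no matching grade | no matching grade |

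The SAP's select table shells include no severity table, so nothing there settles the layout.

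**Step 4: is the information collected?** Yes. Protocol 9.6.6 lists the seriousness criteria among the minimum contents of an initial SAE report. What is missing is a valid grade and a planned display. The underlying data are there.

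**The case against.** The strongest reply is that the problem solves itself. Section 9.6.2.1 says "The Investigator will assess each SAE as either mild, moderate, or severe" and calls the definitions guidelines. The choice is forced, and the first part of the *severe* description, significant interference with usual function, plainly fits these events. Investigators would most likely choose *severe*. The protocol also separates severity from seriousness, and seriousness carries the information on threat to life. SAP 3.6.1 plans no inferential testing of adverse events, so the severity summary is purely descriptive.

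Most of this stands, and it limits the point. It does not remove it. Choosing *severe* contradicts the rest of that grade's own definition, and it still merges life-threatening events with ordinary admissions. Seriousness criteria are collected, but no planned table uses them to separate life-threatening events by arm.

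A reader might infer three stronger things that the documents do not support:

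- *That sites will leave the grade blank or raise queries.* Neither document shows the eCRF field or its edit checks, so this would be speculation.
- *That a mortality difference could be hidden.* All-cause mortality is part of the primary endpoint and is a secondary endpoint, and the SAP reports deaths by arm with cause.
- *That a number of ungraded deaths measures the problem.* The documents give no separate death rate. The pilot figure of 0.94 events per person-year covers death, dialysis and transplant together. A count of deaths would also measure the events that are already reported elsewhere.

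**Conclusion.** The inconsistency is real, and no other section repairs it: a scale meant for every SAE has no definition that fits life-threatening or fatal ones. Every such SAE is affected, however many occur. The practical loss falls mainly on non-fatal life-threatening SAEs, which have no planned by-arm display. The documents give no rate from which to estimate their number.

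The conclusion rests on reading the grade definitions as written. The expectation that these events will be recorded as *severe* is a judgement about practice, based on the forced choice. The effect is confined to descriptive safety reporting. Sample size, power, alpha, the primary analysis and the collection of SAEs are untouched. It is a minor safety-reporting correction.

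**What to change.** 1. **Protocol 9.6.2.1.** Reconcile the grade definitions with 9.6.1.2 so that every SAE has a valid grade. Either remove the exclusion of immediately life-threatening events from *severe*, or add levels above it for life-threatening and fatal events.
2. **SAP 3.6.1.** Derive life-threatening and fatal categories from the seriousness criteria on the SAE report, and show them by arm within the maximum-severity summary. An SAE meeting both criteria should be counted once, as fatal.
3. **SAP section 5.** Add a shell for this table so that the layout is fixed before unblinding.

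Removing the exclusion alone would cure the contradiction, but it would leave non-fatal life-threatening events unseparated. The SAP derivation supplies the missing display whichever protocol option is chosen.

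The cost is a short protocol clarification, one derivation and a few extra table rows. No new data are needed.

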### **9.6.2.2 Relationship to Study Intervention**

The causal relationship of the AE to study drug will be assessed by both the Investigator and the Investigator-Sponsor.

The assessment of causal relationship to study drug should be evidence-based, and not based on the premise that all AEs are possibly causally related to study drug until proven otherwise.

Examples of evidence that would suggest a causal relationship between the study drug and the AE include the occurrence of an AE that is uncommon and known to be strongly associated with drug exposure (e.g., angioedema, hepatic injury, and Stevens-Johnson syndrome) or an AE that is uncommon in the population exposed to the drug.

The causal relationship of the AE is assessed using a binary system, and AEs are classified as either 'related' or 'unrelated'.

- Related: There is 'reasonable possibility' that the study drug caused the AE. The AE follows a reasonable temporal sequence from the time of drug administration. There is supportive evidence (facts) to suggest a possible causal relationship, irrespective of the degree of certainty between the observed AE and the drug.
- Unrelated: An AE does not follow a reasonable temporal sequence from administration of the study drug and/or there is no reasonable possibility that the study drug caused the AE. This assessment includes situations where the AE is related to other factors such as the subject's clinical state, other therapeutic interventions, or concomitant drugs administered to the subject.

Default assessments using the 'related' category without supportive evidence for a causal relationship to study drug is generally uninformative and do not contribute meaningfully to the development of the safety profile of the drug or to subject protection.

#### **9.6.2.3        Expectedness**

The Investigator or Investigator-Sponsor will be responsible for determining whether an AE is expected or unexpected. An AE will be considered unexpected if the nature, severity, or frequency of the event is not consistent with the risk information previously described for the study intervention as described in the current Investigators Brochure.

#### **9.6.3    Time Period and Frequency for Event Assessment and Follow-up**

The Investigator is to report all SAE's either directly observed or spontaneously reported by the study subject. In addition, each study subject will be questioned about SAEs at each visit following initiation of study drug treatment.

#### **9.6.4    Reporting Adverse Events**

Non-serious AEs (with the exception of Adverse Events of Special Interest in Section 9.5.2) will not be collected in source documents or reported in the eCRF.

All SAEs will be collected in source documents and reported in the eCRF.

All Adverse Events of Special Interest will be collected in the source documents and reported in the eCRF.

#### **9.6.5    Reporting Period**

SAE and Adverse Events of Special Interest collection will begin from initiation of study drug treatment through the 30-day follow-up visit. Subjects will be followed for protocol required SAEs and Adverse Events of Special Interest until the final required protocol visit or until all drug-related toxicities and Adverse Events of Special Interest and SAEs have resolved (or are considered chronic/stable), whichever is later.

## **9.6.6 Serious Adverse Event Reporting**

Any SAE, regardless of causal relationship, must be reported to the Investigator-Sponsor within 24 hours after the Investigator or designee becomes aware of the SAE. Compliance with this time requirement is essential so that the Investigator-Sponsor may comply with its regulatory obligations.

The initial SAE report should be completed as fully as possible but should contain, at a minimum:

- Subject number/ID, sex, and age/date of birth;
- The date of awareness;
- The date of report;
- Name of the reporter;
- Name of the suspected medicinal product, if applicable;
- A description of the event, including event term(s), seriousness criteria, and a clinical summary of the event;
- Causality assessment.

Information about all SAEs (either initial or follow-up information) should be collected and recorded in English on the electronic SAE Report Form within the EDC system. The Investigator must provide an assessment of causality (relationship to study drug). If the event meets serious criteria and it is not possible to access the EDC system, a study-specific paper SAE Report Form should be sent to the Investigator-Sponsor via email ([[contact]](mailto:[contact])) within 24 hours of being made aware of the SAE. When the EDC system becomes available, the SAE information must be entered within 24 hours of the system becoming available.

The Investigator must report follow-up information relating to an SAE to the Investigator-Sponsor by updating the electronic eCRF with the new information or by submitting a study-specific paper SAE Report Form in the event that the EDC is not available. When the EDC system becomes available, the SAE information must be entered. The subject should be observed and monitored carefully until the condition resolves or stabilizes.

All deaths are to be thoroughly investigated and reported. Autopsy reports and death certificates are to be obtained, if possible, and summarized as appropriate.

The Investigator-Sponsor and/or its designee are responsible for reporting SAEs to all applicable regulatory agencies and the central ethics committees within the required timeline.

The Investigator is responsible for submitting required safety information to their local Institutional Review Board (IRB) or Independent Ethics Committee (IEC) as per local regulations. This information includes, but is not limited to, any safety alert letter received from the Investigator-Sponsor and any SAEs occurring at their investigative site which meet the reporting requirements of the IRB.

### **9.6.7 Follow-up of Unresolved Events**

All reportable SAEs should be followed until they are resolved, or the Investigator assesses them as chronic or stable or the subject's participation in the trial ends (e.g., until a final report is completed for that subject).

In addition, all SAEs assessed by the Investigator as related to the study drug should continue to be followed even after the subject's participation in the trial is over. Such events should be followed until they resolve or until the Investigator assesses them as "chronic" or "stable". Resolution of such events is to be documented on the appropriate eCRF.

### **9.6.8 Reporting of Pregnancy**

A pregnancy in a female subject must be confirmed by a positive serum or urine test ( $\beta$ -human chorionic gonadotropin).

Female subjects should interrupt study drug if they think they are pregnant. The study drug should be immediately discontinued once the pregnancy of a female study subject has been confirmed. The study drug can be resumed once a negative pregnancy test is confirmed.

If any study subject becomes or is found to be pregnant while receiving study drug or within 30 days of discontinuing the study drug, the pregnancy must be recorded on the study-specific paper Pregnancy Reporting Form within 24 hours of awareness of the pregnancy.

The study-specific paper Pregnancy Reporting Form must be completed with all known information regarding the pregnancy at the time of reporting. Investigative site personnel will update the form with additional information regarding the pregnancy and the outcome of the pregnancy as it becomes available until the outcome of the pregnancy is reported.

The Investigator will follow the subject until completion of the pregnancy. Pregnancy in and of itself is not considered an AE; however, unexpected complications are considered AEs.

Additional information about pregnancy outcomes follows:

- Note that "spontaneous abortion" includes miscarriage and missed abortion.
- All neonatal deaths that occur within 1 month of birth should be reported, without regard to causality, as SAEs. In addition, any infant death after 1 month that the Investigator assesses as related or unrelated to the in-utero exposure to the study drug should also be reported.
- In the case of a live birth, the "normality" of the newborn can be assessed at time of birth.

